1 Includes both CPRD GOLD and Aurum; Observed IRs of 111.5, 66.7, and 26.5 per 100,000 person-years for UTC, bladder cancer, and renal cancer respectively and expected follow-up of 2.4.

2 Observed IRs of 164.5, 104.1, and 58.0 per 100,000 person-years for UTC, bladder cancer, and renal cancer respectively expected follow-up of 2.2.

3 Observed IRs of 161.5, 86.8, and 71.6 per 100,000 person-years for UTC, bladder cancer, and renal cancer respectively expected follow-up of 2.4.

HR=Hazard ratio; UK CPRD=The United Kingdom Clinical Practice Research Datalink

The average follow-up time required to achieve 80% power to detect HRs of 1.5 and 2.0 with the expected number of patients ([Table 6](#)) and observed IRs was evaluated for each of the study outcomes for the country-level analyses ([Table 12](#)) and for a random-effects meta-analysis ([Table 13](#)).

Table 12

Required follow-up time (years) to achieve 80% power in country-level analyses with a type 1 error probability of 5% for different effect sizes for the three primary endpoints given country-level observed incidence rates, expected sample sizes, and expected matching ratios

Matching	Hazard ratio	Urinary tract cancer	Bladder cancer	Renal cancer
UK CPRD¹				
1:3	1.5	3.03	4.73	11.13
	2.0	1.22	1.71	3.54
Sweden²				
1:1	1.5	1.99	2.86	4.73
	2.0	0.96	1.23	1.81
Finland³				
1:2	1.5	2.38	4.00	4.75
	2.0	1.05	1.53	1.75

1 Includes both CPRD GOLD and Aurum; Observed IRs of 111.5, 66.7, and 26.5 per 100,000 person-years for UTC, bladder cancer, and renal cancer respectively, expected number of empagliflozin initiators of 16,360, and matching ratio of 1:3.

2 Observed IRs of 164.5, 104.1, and 58.0 per 100,000 person-years for UTC, bladder cancer, and renal cancer respectively, expected number of empagliflozin initiators of 32,334, and matching ratio of 1:1.

3 Observed IRs of 161.5, 86.8, and 71.6 per 100,000 person-years for UTC, bladder cancer, and renal cancer respectively, expected number of empagliflozin initiators of 18,269, and matching ratio of 1:2.

UK CPRD=The United Kingdom Clinical Practice Research Datalink

Table 13

Required follow-up time (years) in each study country to achieve 80% power for the meta-analysis with a type 1 error probability of 5% for different effect sizes for the three primary endpoints given country-level observed incidence rates, expected sample sizes, and expected matching ratio

Matching	Hazard ratio	Urinary tract cancer	Bladder cancer	Renal cancer
UK CPRD¹				
1:3	1.5	1.38	2.05	3.08
	2.0	0.74	0.91	1.20
Sweden²				
1:1	1.5	1.38	2.04	3.07
	2.0	0.74	0.91	1.20
Finland³				
1:2	1.5	1.50	2.22	3.35
	2.0	0.81	0.99	1.31

1 Includes both CPRD GOLD and Aurum; Observed IRs of 111.5, 66.7, and 26.5 per 100,000 person-years for UTC, bladder cancer, and renal cancer respectively, expected number of empagliflozin initiators of 16,360, and matching ratio of 1:3.

2 Observed IRs of 164.5, 104.1, and 58.0 per 100,000 person-years for UTC, bladder cancer, and renal cancer respectively, expected number of empagliflozin initiators of 32,334, and matching ratio of 1:1.

3 Observed IRs of 161.5, 86.8, and 71.6 per 100,000 person-years for UTC, bladder cancer, and renal cancer respectively, expected number of empagliflozin initiators of 18,269, and matching ratio of 1:2.

UK CPRD=The United Kingdom Clinical Practice Research Datalink

Based on the feasibility assessment before this study and the interim reports, utilization of empagliflozin in the UK and Sweden is still low. Accrual of empagliflozin users is monitored in the data sources as described in [Section 8.7.1.7](#). The number of users in each treatment cohort has been monitored at 24 months after empagliflozin use started being captured in the UK and Swedish data sources (November 2016) and has and will be monitored annually thereafter until November 2020. The numbers were reported in annual interim reports in the 1st quarter of years 2017-2021 and the results of the interim reports were submitted to EMA by the Sponsor within the earliest corresponding PBRER. Initially, this study included two countries, the UK (CPRD GOLD) and Sweden, with follow-up until 31st December 2019. In order to increase the accumulated patient years and number of patients initiating the study drugs as well as accounting for the long latency period related to risk of malignancies, the study follow-up was first extended until 31st December, 2020 and Finnish national registers were included. Additionally, in this version of the protocol (Version 7.0) CPRD Aurum was included and the study period for both CPRD databases was extended to 31st December, 2021 in order to further increase the sample size and follow-up, and, consequently, study power.

8.6 DATA MANAGEMENT

Full audit trail starting from raw data obtained from register holders and ending with statistical tables and graphs in reports will be maintained. Data management, tabulations, graphics, and statistical modelling will be carried out with R data analyses language (<http://www.r-project.org>). R language is described more detailed in report "R: Regulatory Compliance and Validation Issues: A Guidance Document for the Use of R in Regulated Clinical Trial Environments" (<http://www.r-project.org/doc/R-FDA.pdf>). Source code of data management and data analyses is kept for inspection for five years after publication of results. The study may be inspected by the sponsor's study independent representative(s) or inspected by the competent authorities. A SEAP detailing all statistical analyses will be drawn and used as a basis for analysis.

Data from multiple country sources will be sent utilizing password protected media. All study related datasets will be stored in secured server environment. Access to data will be permitted only to study statisticians and data managers in line with the data permits. All data used for this study will be anonymous such that no study individual can be directly identified. Data will be regularly backed-up and stored in a separate secure location. All data and back-ups will be maintained within the EU.

8.7 DATA ANALYSIS

The final approach to data analysis will be presented in a separate SEAP to be developed prior to the start of data analysis. The SEAP will include a detailed algorithm for identifying T2D patients, detailed methods for covariate selection, checking for empirical equipoise, model checking for outcome models, methods for time-dependent exposure and time-varying confounding, the approaches for handling missing data, the assessment of the potential impact of unmeasured confounding, and the critical sensitivity analyses. The SEAP will be made available upon request to EMA and will be included or appended in the study report.

8.7.1 Main analysis

For the primary, secondary and further objectives, the main data analysis will be conducted in two stages: (i) construction of the PS-matched cohort by modelling the exposure to empagliflozin vs. DPP-4 inhibitors and (ii) estimating the effect of exposure to empagliflozin on the urinary tract (bladder, renal and other) cancers using aHRs and IRs compared to those exposed to DPP-4 inhibitors. Additional sensitivity analyses will be performed to validate the robustness of alternative definitions of outcome, exposure, covariates and reduction of bias due to matching.

8.7.1.1 Matching at index date

For all individuals, PS for the comparison of empagliflozin vs DPP-4 inhibitors will be computed at the index date as the probability to receive empagliflozin conditional on treatment and clinical history up to index date within each stratum. The PS will be estimated

using a binary logistic regression model. Depending on sample size, combination exposures with metformin will be accounted for through separate PS, stratification, or adjustment.

The selection of variables to be included in the PS models (see [Section 8.3.3](#)) will be based on scientific basis from previous studies, clinical/epidemiological significance and examination of exposure group differences in the distribution of each covariate. The covariates included in the PS model should ideally be associated with the outcomes of interest. Simulation studies show that variables that are unrelated to the exposure but are related to the outcome should always be included in the estimation of PS [[R12-1913](#)]. Inclusion of these variables increases the precision of the estimated effect of exposure without increasing bias. In contrast, inclusion of variables that are related to the exposure but not to the outcome can decrease precision of the estimated effect of exposure without decreasing bias. The variables listed in [Annex 6](#) are potential candidates for inclusion in the PS model. Depending on sample size, combination exposures with metformin and treatment complexity (monotherapy, dual combination therapy, triple combination therapy) will be accounted for through separate PS, stratification, or adjustment.

Matching will be performed for empagliflozin initiators with patients initiating DPP-4 inhibitors within each country database. Matching will be carried out in several rounds to achieve the highest possible matching ratio given the available data in each country (up to 1:3 matching) [[P12-07757](#)]. In the first round of matching, for each empagliflozin initiating individual i with a particular index date T_{iE} , all individuals initiating other DPP-4 inhibitors within three months before or after T_{iE} will be chosen. Of these, one individual with the closest PS to that of i within a predefined PS interval will be selected as a match (Greedy matching method). The predefined PS interval will be calculated based on the standard deviation of the logit of PS (δ) multiplied by some coefficient k (say, $k\delta$, when $k=0.2$). The value of the coefficient k will be calibrated to ensure at least 99% of those exposed to empagliflozin have matches from each comparator. The selected comparators are then removed from the pool of the possible comparators for further selection (sampling without replacement). Once the first round of matching is done, additional rounds of matching will be carried out to identify a second and possibly a third match for each already matched for each empagliflozin initiating individual (variable ratio matching with 1:3 as the maximum ratio). The number of matched DPP-4 inhibitors, and hence the overall matching ratio, will therefore be maximized within each country. Matching by time period, based on index dates, enables better control of time-varying confounders including changing prescription patterns for empagliflozin and potential confounding.

8.7.1.2 As-treated (AT) analysis

For the incident users of empagliflozin along with their respective matches, the primary analysis will be performed using the AT approach. This corresponds to censoring individuals who discontinue use of the index drug, i.e., either switch from the index drug to other drugs (empagliflozin, DPP-4 inhibitors, or other SGLT-2 inhibitors) during follow-up, or stop using the index drug (see [Section 8.3.4](#)).

8.7.1.3 Population summary and descriptive analyses

Univariate and bivariate distribution of exposures, outcomes and relevant covariates will be presented using absolute and relative frequencies for categorical variables and summary measures for continuous variables (mean, standard deviation, median, min, max). Bivariate distributions for outcomes and covariates will be with reference to primary exposure definitions.

Absolute risks (IRs) for the defined outcomes will be estimated within each exposure category and key covariates using Poisson regression. The IRs will be presented along with 95% CIs. Other descriptive summaries such as number of events and person-time for calculating the IR will be included.

Kaplan-Meier plots, with 95% CIs, for survival probabilities will be presented for all urinary tract cancers, bladder cancers and renal cancers with primary exposures using the AT definition of follow-up times.

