8.3.4 Censoring of follow-up time

The following events lead to censoring: all-cause mortality, emigration, patient transfer, meeting specific exclusion criteria (see exclusion criteria in [Section 8.2.5](#)) and end of study period. Follow-up times will be censored at any of these events, whichever occurs first. In the primary AT analysis discontinuation of index drug treatment is an additional censoring variable. Treatment discontinuation is defined either by

- A switch from the index drug to any other drugs (empagliflozin, DPP-4 inhibitor, or other SGLT-2 inhibitor), or to a fixed-dose combination of a SGLT-2 inhibitor with a DPP-4 inhibitor (identified from the ATC class A10BD) plus a 3-month period following the switch, or
- As the stop date plus a 3-month period following it. The stop date is the end date of the first continuous exposure period of the index drug, where continuous treatment is defined as having consecutive prescriptions separated by 30 days or less ([Figure 1](#)).

The 3-month period after the switch or the stop date is used to allow for a delay in the diagnosis of cancer [[R16-2539](#)]. In a sensitivity analysis this time period is extended to 6 months.

Switch to a fixed-dose combination including the same index drug and drugs other than DPP-4 inhibitors and SGLT-2 inhibitors is not considered a censoring variable (for example, switch from sitagliptin to a fixed-dose combination including sitagliptin and pioglitazone).

[figure not shown]

Figure 1

Discontinuation of index drug due to stopping of index drug or switching of index drug. In the primary analysis follow-up is censored at treatment discontinuation.

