
ANNEX 5. CODES TO IDENTIFY THE OUTCOME VARIABLES

The codes will be updated for the data applications.

No.	Variable	ICD-10 / ICD-O-3 codes	READ codes	Outcome / Censoring variable	Analyses ¹
1	Urinary Tract cancer (malignant and carcinoma in situ)	C64-C68 D09.0, D09.1	Byu9, B837, B83z, B4A, B49	Outcome	D, P, S, F, NCC, MSM Sens
2	Bladder cancer (malignant and carcinoma in situ)	C67, D09.0	B49, B837, selected BB4 codes	Outcome	D, P, S, F, Sens
3	Renal cancer (malignant)	C64, C65	B4A0, B4A1	Outcome	D, P, S, F, Sens
4	Other urinary tract cancer (non-renal, non-bladder cancers) – sensitivity (malignant)	C66,C68	Byu9	Sensitivity outcome	D, Sens
5	Urinary Tract cancers from GP data (CPRD only) – sensitivity		Byu9, B837, B83z, B4A, B49	Sensitivity outcome	Sens
6	Urinary tract neoplasms of uncertain or unknown behaviour - sensitivity	D41	B917, B91z, BA04	Sensitivity outcome	Sens
Censoring variables					
7	Other non-UT cancers	C00-C99, D00-09 (excl. C64-68, D09.0, D09.1)	B (excl. Byu9, B837, B83z, B4A, B49, B49, B837, selected BB4 codes)	Censoring	
8	End of study period			Censoring	
9	End of GP practice coverage			Censoring	
10	Use of other SGLT-2 (since start of follow-up)			Censoring	
11	Use of fixed-dose combinations of			Censoring	

No.	Variable	ICD-10 / ICD-O-3 codes	READ codes	Outcome / Censoring variable	Analyses ¹
	SGLT-2 inhibitors with DPP-4 inhibitors				
12	Patient transfer			Censoring	
13	End stage renal disease / renal dialysis			Censoring	
14	All-cause mortality (excluding UT cancer mortality)			Censoring	
15	Discontinuation of primary exposure			Censoring for as-treated analysis	
16	UT cancer characteristics (based on staging, TNM codes, etc)			Sensitivity outcome / descriptive	D, Sens

1 D=Descriptive, P =Primary , S = secondary, F = further, Sens = sensitivity, NCC =Nested-case-control, MSM – marginal structural models

**ANNEX 6. COVARIATES TO BE CONSIDERED FOR INCLUSION IN
THE PROPENSITY SCORE MODEL.**

No.	Variable
Socio-demographic variables	
1	Age
2	Sex
3	Socioeconomic status
4	Calendar year of index date
5	Duration of look-back period
6	Duration of treated diabetes at index date
Diabetic complications	
7	Diabetic retinopathy or diabetic maculopathy
8	Diabetic nephropathy
9	Diabetic neuropathy
10	Peripheral vascular disease
11	Diabetic lower limb severe complications
Urinary tract related comorbidities	
12	Kidney or genitourinary stones
13	Prior history of UTI or pyelonephritis
14	Liver disease
15	eGFR
16	Renal impairment

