5.1.3. EXPOSURE TIME

Time at risk will start on index date and continue until first treatment discontinuation (see definition in Section 5.1.6). Continuous exposure will be defined as successive exposure periods for the study drugs separated by gaps of 30 days at most. Duration of exposure

Proprietary confidential information © 2024 Boehringer Ingelheim International GmbH or one or more of its affiliated companies

episodes for individual prescriptions of study drugs will be derived based on package size, unit strength and daily dose.

To account for an empirical induction/promotion period of cancer, a latency period of 6 months (180 days) after the index date is applied. Patients with less than 6 months (180 days) of follow-up time will be excluded. In addition, patients with any diagnosis of any cancer within the latency period will be excluded. In a sensitivity analysis, the latency period will be extended to 12 months (365 days).

* Other drugs: a prescription of another drug (empagliflozin, a DPP-4 inhibitor, or a SGLT-2 inhibitor) other than index drug

Figure 1 Definition of continuous exposure period of index drug

For the primary AT analyses, the time at risk will begin after the latency period and end at urinary tract (bladder, renal or other) cancer or at any of the censoring events (listed in Table 4), whichever occurs first. In addition, treatment discontinuation of the index drug (defined in Section 5.1.6) is an additional censoring variable.

For the sensitivity ITT analyses, the time at risk will begin after the latency period and end at urinary tract (bladder, renal or other) cancer or any of the censoring events excluding treatment discontinuation of the index drug.

Patients with censored time at risk will not be able to re-enter the study cohort at a later time point. The time at risk will not be censored if oral or injectable glucose-lowering drugs other than the index drugs and SGLT-2 inhibitors are prescribed in addition to empagliflozin or a DPP-4 inhibitor after the index date.

Proprietary confidential information © 2024 Boehringer Ingelheim International GmbH or one or more of its affiliated companies

Table 4 Censoring events.

Censoring event	Definition	Data source
All-cause mortality	Censoring of follow-up time occurs at the date of death regardless of the cause. Applied in all analyses.	UK: CPRD-GOLD and Aurum Sweden: Cause of death register Finland: Cause of death register

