Emigration from the study country	Censoring of follow-up time occurs at the date of emigration from the study country. Applied in all analyses.	UK: CPRD-GOLD and Aurum Sweden: Total population register ¹ Finland: Population register centre
Patient transfer	Censoring of follow-up time occurs at the date of patient transfer. Applied in all analyses.	UK: CPRD-GOLD and Aurum Sweden: NA Finland: NA
Incidence of any cancer during follow-up	A registered diagnosis of any cancer (excluding non-melanoma skin cancer) during follow-up. (ICD-10, ICD-7, ICD-O-3 and READ diagnosis codes in Annex I) Applied in all analyses.	UK: CPRD-GOLD and Aurum Sweden: Swedish cancer registry (SCR) Finland: FCR
Diabetes diagnosis other than type 2	A diagnosis of type 1 diabetes or other non-type 2 diabetes during follow-up identified using the same algorithm as used for the exclusion criteria (Section 4.2.4) Relevant ICD-10 codes and READ diagnosis codes are provided in Annex I. Applied in all analyses.	UK: CPRD and Aurum Sweden: NDR, NPR Finland: reimbursement registry
End of study period	Censoring of follow-up time occurs at end of study date i.e. 31 December 2020 (2021 for UK-CPRD). Applied in all analyses.	NA

Proprietary confidential information © 2024 Boehringer Ingelheim International GmbH or one or more of its affiliated companies

Treatment discontinuation (AT exposure- main analysis)	Censoring of follow-up time occurs 90 days after 
 - last day of medication (i.e. stop date) - new prescription of the other study drug or of a SGLT-2 inhibitor Applied only in analyses using the AT exposure definition.	UK: CPRD-GOLD and Aurum Sweden: SPDR Finland: FPR
Treatment discontinuation (AT exposure- sensitivity analysis)	Censoring of follow-up time occurs 180 days after 
 - last day of medication (i.e. stop date) - new prescription of the other study drug or of a SGLT-2 inhibitor Applied only in the sensitivity analysis using the AT exposure definition.	UK: CPRD-GOLD and Aurum Sweden: SPDR Finland: FPR

¹ The National patient register will be used if data on immigration/emigration are unavailable from the Total population register.

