6.7. AS-TREATED ANALYSIS

6.7.1. Descriptive analysis

Crude incidence rates (IRs) for the outcomes defined in Table 8 will be estimated within each exposure category as defined in Table 5 using Poisson regression.

In addition, stratified IRs will be derived for the following variables:

- Demographics and other baseline characteristics at index date Table 11.

Proprietary confidential information © 2024 Boehringer Ingelheim International GmbH or one or more of its affiliated companies

- Diabetic complications Table 12.
- Non-diabetic concomitant disease Table 13.
- Diabetic concomitant medication use Table 14.
- Non-diabetic concomitant medication use Table 15.

Crude IRs will be presented along with 95% CIs. Other descriptive summaries such as number of events and person-time for calculating the IR will be included. Analysis will be performed for each country. Results will be reported as in Table 22.

Kaplan-Meier plots, with 95% CIs, for event-free survival probabilities will be presented for each country for the outcomes defined in Table 8 with exposures as defined in Table 5. Results will be reported as the figure template shown in Figure 6.

Meta-analyses of IRs will be carried out using aggregated data across countries as described in Section 6.7.3.1 and reported as shown in Table 22.

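### The planned Kaplan-Meier curves censor death and other first cancers, so one minus the curve modestly overstates the cumulative probability of each cancer, and the event-free survival label is inaccurate

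*Protocol*

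**What the plan says.** **The display.** Protocol 8.7.1.3 plans this figure on as-treated follow-up: "Kaplan-Meier plots, with 95% CIs, for survival probabilities will be presented for all urinary tract cancers, bladder cancers and renal cancers". SAP 6.7.1 repeats it: "Kaplan-Meier plots, with 95% CIs, for event-free survival probabilities will be presented for each country", for the three Table 8 outcomes, with Figure 6 as the template. SAP Table 16 counts nine such figures (three outcomes in three countries), drawn in the matched cohorts.

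**What is censored.**
- Death. Protocol 8.3.4: "The following events lead to censoring: all-cause mortality, emigration, patient transfer, meeting specific exclusion criteria". SAP Table 4 (section 5.1.3): "Censoring of follow-up time occurs at the date of death regardless of the cause", applied in all analyses.
- Other first cancers. SAP Table 4 lists as a censoring event: "A registered diagnosis of any cancer (excluding non-melanoma skin cancer) during follow-up", again in all analyses. Protocol Annex 5 has a censoring row headed "Other non-UT cancers".
- Other urinary tract sites. Protocol 8.3.5 and SAP 5.1.3 end time at risk at any urinary tract cancer. A first renal cancer therefore removes the patient from the bladder curve, and the reverse.

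**What is absent.** The available text names no competing-risk estimator, and Table 16 lists none. For absolute risk, protocol 8.7.1.3 names the Poisson incidence rate, not the curve.

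**The concern.** Kaplan-Meier treats a censored patient as still able to have the event later, at the same rate as those who remain. That suits the administrative end of the study. It does not suit death, after which the cancer cannot occur, or another first cancer, after which the plan's own follow-up rule no longer counts it. With such events censored, 1-KM estimates the risk in a population where competing events do not happen, and no objective of this study asks about that population.

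These plots are the only cumulative display of the outcomes by drug in the available list of analyses. In a regulatory cancer-safety study, readers will take absolute risk from them. If competing rates differed between the arms, the curves would also hide a difference in actual risk. The event-free label invites a second misreading, since patients who have died or had another cancer are not counted as having had an event.

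**Working it through.** **Inputs from the documents (Sweden)**
- Urinary tract cancer: 346 events in 210,329 patient-years (protocol 6.1.1). 346 / 210,329 × 100,000 = 164.5, which matches the stated rate, so h = 0.001645 per year.
- Bladder 104.1 and renal 58.0 per 100,000; 219 / 210,329 and 122 / 210,329 reproduce both.
- Average follow-up: 2.2 years (protocol 8.5).
- Longest post-lag follow-up in the empagliflozin arm: protocol Table 6 shows no eligible Swedish empagliflozin initiators in 2014. The earliest start is therefore January 2015. To 31 December 2020 is 6.0 years; less the 6-month lag, about 5.5 years.

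**Assumption, not in the documents.** Competing rate c (death plus other first cancer) of 2 to 5.5 per 100 person-years. All hazards are taken as constant.

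**Formulas**
- 1-KM with competing events censored: 1 − exp(−h·t)
- Cumulative incidence: h/(h+c) × [1 − exp(−(h+c)·t)]

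**Urinary tract cancer, t = 2.2**
- 1-KM = 1 − exp(−0.003619) = 0.361%
- c = 0.02: 0.001645/0.021645 × [1 − exp(−0.047619)] = 0.353%
- c = 0.055: 0.001645/0.056645 × [1 − exp(−0.124619)] = 0.340%
- Excess: 0.008 to 0.021 percentage points, or 2% to 6% relative

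**Urinary tract cancer, t = 5.5**
- 1-KM = 1 − exp(−0.0090475) = 0.901%
- c = 0.02: 0.001645/0.021645 × [1 − exp(−0.1190475)] = 0.853%
- c = 0.055: 0.001645/0.056645 × [1 − exp(−0.3115475)] = 0.777%
- Excess: 0.048 to 0.123 percentage points, or 6% to 16% relative

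**Bladder and renal, t = 5.5.** Here the remaining urinary tract cancers (164.5 − 104.1 = 60.4 and 164.5 − 58.0 = 106.5 per 100,000) are added to c.
- Bladder: 0.571% against 0.540% to 0.492%
- Renal: 0.318% against 0.301% to 0.274%
- The relative excess is again about 6% to 16%.

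**The label, t = 5.5.** The plotted survival would be 100% − 0.90% = 99.1%. The proportion free of both the cancer and the competing events is exp(−(h+c)·t) = 88.8% (c = 0.02) or 73.2% (c = 0.055).

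**Illustration of unequal arms (hypothetical).** With a true hazard ratio of 1 and c = 0.02 in one arm and 0.04 in the other, both Kaplan-Meier curves give 0.901% at 5.5 years. The cumulative incidences are 0.853% and 0.809%.

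**Simulation check of the formulas.** With 2,000,000 simulated patients, c = 0.03 and 6 years, 1-KM was 0.99% and the proportion with the cancer 0.91%. The formulas give 0.98% and 0.90%.

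**The case against.** **The figure carries no inference.** The primary objectives ask for adjusted hazard ratios and incidence rates. Poisson rates are reported by exposure group and pooled, and neither they nor the cause-specific Cox hazard ratios are invalidated by this censoring. No test or pooled estimate uses the curves, and neither document says 1-KM will be read as a patient's risk. All of this stands and limits the point to a descriptive display.

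**The excess is small.** At average follow-up it is about 0.01 to 0.02 percentage points. The 95% CI on the whole-population Swedish rate (148.1 to 182.8 around 164.5) is already about −10% to +11%, and each matched arm's curve should be less precise. The larger relative figures belong to a sparse tail: 629 of 32,334 Swedish empagliflozin initiators (1.9%) started in 2015. This also stands.

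**Aalen-Johansen curves would still be hypothetical**, because as-treated discontinuation remains a censoring event. True, but that censoring defines the as-treated question. Censoring death and other first cancers does not, so this does not rebut the change.

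**A competing-risk analysis may be planned elsewhere.** The SAP text between 6.7.3.2 and 6.10 is not available, so this cannot be fully excluded. Table 16 makes it unlikely.

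**Stronger readings the documents do not support.** A reader might infer that the survival curves themselves are too high as a statement about cancer risk. Read that way they are too low; it is the complement that is too high. A reader might also infer that the comparison of the drugs is biased. The hazard ratios are not, and no figure in the documents shows competing rates differing between the propensity-matched arms.

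**Conclusion.** The point holds as a minor improvement to a descriptive figure. Censoring death and other first cancers makes 1-KM at least as large as the cumulative incidence, and larger once competing events occur. That direction does not depend on the assumed rate. The event-free label is inaccurate because those competing events do not count as events in the curve.

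The size does depend on assumptions: constant hazards, a competing rate of 2 to 5.5 per 100 person-years that the documents do not give, and interim-report incidence rates standing in for those of the matched cohorts. On that basis the relative overstatement in Sweden is 2% to 6% at average follow-up and 6% to 16% at about 5.5 years, at most about 0.12 percentage points.

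**What to change.** In protocol 8.7.1.3 and in SAP 6.7.1, Table 16 and Figure 6:
- Replace the Kaplan-Meier plots with Aalen-Johansen cumulative incidence curves and 95% CIs, by exposure group and country.
- Treat death and first other cancer as competing events. For the bladder and renal curves, include the other urinary tract sites.
- Keep administrative end of study, transfer, emigration and as-treated discontinuation as censoring.
- Drop the event-free survival label. Add a footnote that the curves describe risk under the as-treated definition and do not map one-to-one to the cause-specific hazard ratio.

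The Cox and Poisson analyses stay as they are.

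The cost is a change of estimator in R, the planned software, using event dates the study already needs for censoring. What is lost is the direct correspondence between curve and hazard ratio, which the footnote covers. If the Kaplan-Meier plots are kept, the minimum is a label stating that death and other cancers are censored and that 1-KM is not the probability of the cancer.
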